### **3.5. Study Endpoints**

#### **3.5.1. Primary Endpoint**

The primary response variable is GC responsiveness, defined as the lowest dose of prednisone at which eosinophils remain  $<1000/\mu\text{l}$ , for at least two consecutive weekly blood draws, and at which symptoms are controlled as determined by the investigator; OR, dose of prednisone at which subject is unable to taper prednisone further without rebound of eosinophilia and/or symptoms after three attempts; OR, the challenge dose, if there is no drop in eosinophil counts within the first week of challenge or taper.

GC responsiveness in each individual will be assessed using the percent change in eosinophil count (eosinophil response rate [ERR]) from baseline to 4h (or 24h) post-steroid challenge.

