## Précis

This study aims to develop a model to determine whether a single, oral, weight-based dose of glucocorticoid (GC) can predict clinical and biologic response to GC's over the long term in subjects with hypereosinophilic syndrome (HES). Subjects with FIP1L1/PDGFR $\alpha$ -negative HES, who are symptomatic with eosinophil count  $>1500/\mu\text{L}$  and receiving  $\leq 10$  mg prednisone daily, will be enrolled. A single oral dose of prednisone (1 mg/kg rounded to the nearest 5mg) will be administered. Eosinophil count and various laboratory parameters will be assessed at 2 hours, 4 hours and 24 hours following prednisone administration (investigators will be blinded to the results of the eosinophil counts). The subjects will then begin GC therapy at 30 mg prednisone daily followed by a standardized taper. The lowest dose of GC at which symptoms and eosinophilia are controlled will be compared to the change in eosinophil count at 2, 4 and 24 hours post-challenge. Mechanisms and in vitro correlates of GC resistance will also be explored.

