### **1.2.3. Glucocorticoid effects on trafficking and eosinophil transcriptomics**

At the time of initiation of this study, early (<4h) kinetics of glucocorticoid action on eosinophils were not well described. Samples from this and other studies were subjected to transcriptomic evaluation to determine early kinetics of eosinophil decline. More recent knowledge suggests that there is a substantial decline of eosinophils in the peripheral circulation (at least in normally responsive eosinophils) by 3 hours. More striking, the major genes of interest in apoptosis and trafficking were noted to be up or down-regulated by 2 hours after GC administration. Of the 414 genes differentially expressed in eosinophils in the first 2 hours after prednisone administration, 12 are known to be involved in leukocyte migration: *CXCR4*, *RIPOR2*, *PREX1*, *CCR1*, *PTGER4*, *SWAP70*, *IL16*, *PIK3CG*, *NLRP12*, *CD244*, *S1PR1*, and *CSF1*. Four of these genes were significantly differentially expressed prior to the initial decline in circulating eosinophils, which occurred in the interval between 60 and 120 minutes. In vitro and flow cytometric studies demonstrated that *CXCR4* is upregulated in response to steroids and we hypothesize this might be important in trafficking of eosinophils from the peripheral blood into tissues (14). For this reason, we are splitting amount of research blood drawn in the 4 hour timepoint into a 2 and 4 hour timepoint in order to be able to study the exploratory endpoints without losing valuable data at the 4 hour timepoint. The primary clinical endpoint at 4 hours remains unchanged as it is not appropriate or possible to change the primary endpoint at this juncture.

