The primary objective of this study is exploratory, because we are looking for the best model for prediction and do not want to limit ourselves to 1 class of models. In order to protect ourselves from creating a model that appears to predict the response when in fact there is no real relationship between the predictors and the response, we will first test for a significant Spearman correlation between GC responsiveness and ERR to make sure that there is a significant effect. If there is a significant correlation, then we have some comfort that our final model is not just modeling noise. For our sample size justification (section 6.2), we assume that if we have a large enough sample size to show a significant correlation between GC responsiveness and 1 of the continuous predictive variables, then we would have a sample size large enough to explore these models. Because our objective is to find a reasonable model, and sample sizes are limited by availability of subjects, the sample size calculation is mostly to ensure that with such small sample sizes we would be able to detect moderate (i.e., correlations of about 0.5) effects.

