## 6.2. Sample Size Justification

The sample size of this study is practically limited by the number of subjects available for study. Currently, about 30-35 new hypereosinophilic subjects per year are seen at the NIH and enrolled on protocol 94-I-0079, of which approximately 10% would meet inclusion criteria for this protocol. Consequently, we expect that we can enroll 30-40 subjects in this study over a 13-year period.

To show that this number of subjects is not unreasonably small, we calculate the sample size for a Spearman's correlation coefficient. If true correlation is 0.5 between a predictor variable (ERR at 4 or 24 hours) and the GC responsiveness (see Description of the Study, Section 3.1), the total number of subjects needed to show that the correlation is different from zero at the two-sided 0.05 level with 80% power is about 32 subjects. We calculated this by simulating 10,000 data sets of 32 bivariate random normal variables with correlation 0.5 and seeing that the Spearman coefficient is significantly different from zero 79.5% of the time. This is similar to the usual sample size calculation for Pearson's correlation(17) or (18) that gives a sample size of 29 for the same situation.

Because the predictor and outcome variables are both continuous, if the true change in the dependent variables is 0.5 standard deviations per 1 standard deviation change in the independent variable, a clinically important measurement of association between response to a steroid challenge and final required dose of GC will be possible.

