## 6.3. Final Analysis Plan

### 1. Study Endpoints:

- Primary: GC responsiveness.
  - Definition: See primary endpoint for definition of GC responsiveness.
  - Validity and Reliability: This is a rare disease, and standard care for this disease is still being developed. There is no standard endpoint, and this endpoint has not been used before. One of the purposes of this study is to see if this endpoint can be reliably predicted. The endpoint has face validity because the dose that controls eosinophil concentration is useful for determining the extent of a subject's disease and their responsiveness to steroid therapy. We will first try and predict GC responsiveness as described in section "Description of the Analyses" (Section 6.1), but may also try to predict the categorization of the GC responsiveness into 3 ordered categories described in section "Description of the Analyses".
  - Predictor Variables: All predictor variables will be measured in the first 24 hours after initial dose, and will be blinded to the PI and Accountable Physician. These variables will be used to predict the GC responsiveness:

percent change in eosinophil count from baseline to 4 and 24 hours and steroid absorption.

- Secondary:
    - Classification of subjects by GC response for assessment of clinical factors associated with GC responsiveness (including HES variant, pattern of organ involvement and laboratory parameters)
  - Exploratory
    - Exploratory analyses of potential mechanisms and in vitro correlates of GC resistance, including impaired steroid absorption, cell surface markers on lymphocytes, intracellular and serum cytokine profiles.
2. Description of the Statistical Methods to Be Employed:
    - Spearman correlation of GC responsiveness and percent change in eosinophil from baseline to 4 and 24 hours, with confidence intervals and testing whether it is different from zero.
    - Model building as described in section “Description of the Analyses” (Section 6.1).
  3. Level of Significance to be Used: Two-sided 0.05
  4. Exploratory Analyses: See section 6.1 for primary objective. Similar model building strategies will be used for secondary endpoints and exploratory endpoints.

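### The Spearman check is planned at both 4 h and 24 h, each at 0.05, with no time point designated, so a false pass has a chance of about 7–10% rather than 5%

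*Combined protocol and SAP*

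**What the plan says.** The time point for ERR differs between sections of the combined protocol and SAP:

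- **4 h only.** Section 1.2.3: "The primary clinical endpoint at 4 hours remains unchanged as it is not appropriate or possible to change the primary endpoint at this juncture". The interim model in Section 6.4 is built on log(ERR) at 4 h.
- **4 h or 24 h.** Section 3.5.1: "from baseline to 4h (or 24h) post-steroid challenge". Sections 6.1 and 6.2 also speak of 4 or 24 hours.
- **4 h and 24 h.** The null hypothesis in Section 6.1.2 covers both times. The methods in Section 6.3 list a "Spearman correlation of GC responsiveness and percent change in eosinophil from baseline to 4 and 24 hours", with confidence intervals and a test against zero.
- **2, 4 and 24 h.** The Précis says the lowest controlling dose "will be compared to the change in eosinophil count at 2, 4 and 24 hours post-challenge".

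The purpose of the test is given in Section 6.1: "we will first test for a significant Spearman correlation between GC responsiveness and ERR to make sure that there is a significant effect". A significant result is meant to give some comfort that the final model reflects more than noise. Section 6.3 sets one level: "Level of Significance to be Used: Two-sided 0.05". Section 6.2 sizes a single correlation of 0.5, for which the number needed at the "two-sided 0.05 level with 80% power is about 32 subjects". Section 6.1.2 adds that model building will be attempted whether or not the test is significant.

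**The concern.** The final analysis has two Spearman tests at 0.05 each. The plan does not say which one is the check, does not divide the 0.05 between them, and has no rule for the case where only one is significant. The sizing argument in Section 6.1 is framed around significance for one of the continuous predictors, so a reader could fairly treat a pass at either time as enough.

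Section 6.1 leaves the class of models open and relies on this test to show that the chosen model rests on a real relationship. If the test passes by chance more often than 5%, a significant result is weaker support than it appears. The choice of which result to emphasise, a same-day 4 h count or a next-day 24 h count, would also be open after the data are seen.

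**Working it through.** **Inputs from the documents.** Two-sided 0.05 with no split (Section 6.3); 32 subjects, true correlation 0.5, simulated power 79.5% and a Pearson cross-check of 29 (Section 6.2); expected enrolment 30–40 (Section 6.2) with a ceiling of 40 (Protocol Summary); two tests, at 4 h and 24 h (Sections 6.1.2 and 6.3).

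**Assumptions.** The correlation between 4 h and 24 h ERR is not given, so 0 to 0.95 was tried. A pass is taken to mean significance at either time. Data are continuous normal, as in the plan's own simulation.

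**Step 1: reproduce the plan's figure.** With 200,000 bivariate normal data sets at correlation 0.5 and n = 32, Spearman's coefficient tested by its t approximation is significant in 80.1%, against 79.5% stated. For Pearson, n = ((1.960 + 0.842) / atanh(0.5))² + 3 = (2.802 / 0.549)² + 3 ≈ 29.0, against 29 stated. Both agree. They apply to one test.

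**Step 2: false pass with two unrelated tests.** 1 − (1 − 0.05)² = 1 − 0.9025 = 9.75%.

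**Step 3: false pass with two correlated tests.** GC responsiveness was simulated independently of two ERRs that are correlated with each other (n = 32, up to 200,000 data sets per setting). Where repeated runs differ slightly, the range is shown.

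| Correlation between 4 h and 24 h ERR | Chance that at least one test is significant |
|---|---|
| 0 | 9.8% |
| 0.5 | 9.2% |
| 0.7 | 8.5–8.7% |
| 0.9 | 7.3–7.4% |
| 0.95 | 6.8% |

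At n = 40 the results are within about 0.2 percentage points of these. The rate is above 5% throughout the range.

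**Step 4: the two ways to restore 5% for the final test.**

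- One designated time point at 0.05: power 80.1% at n = 32, unchanged.
- Both time points at 0.05 / 2 = 0.025: power per test 71.1% at n = 32 and 82.1% at n = 40. Power is 79.7% at n = 38 and 81.0% at n = 39, so about 39 subjects are needed.

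**The case against.** The best case for the plan has four parts.

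1. **The primary objective is called exploratory and the test gates nothing.** This stands, and it limits the harm. Section 6.3 gives a significance level and does not claim a family-wise error rate. A reader might infer that a false pass would wrongly let the modelling go ahead, but Section 6.1.2 rules that out.
2. **The wordings can be reconciled.** The phrases with *or* and with *and* can be read as two pre-specified candidate predictors, both reported with confidence intervals. The sentence in Section 1.2.3 explains the added 2 h draw and does not mention 24 h. This has force: no result is planned to be hidden, and any later choice would be one of emphasis. It still leaves unsaid which test provides the comfort described in Section 6.1.
3. **The 2 h value is not a planned test.** This also stands. From the Précis a reader might infer three chances to pass, up to 1 − 0.95³ = 14.3%. However, Section 1.2.3 ties the 2 h sample to exploratory endpoints, and Sections 3.5.1, 6.1, 6.1.2, 6.2 and 6.3 all leave 2 h out of the predictor and the test.
4. **A check at 4 h does not protect a model built on 24 h ERR.** Correct. Designating 4 h is only a complete answer if the plan also says this.

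**Conclusion.** The point holds in a limited form. As written, the final analysis has two tests at 0.05 and no designated time point. If either may count, the chance of false reassurance is about 7–10% instead of 5%. This rests on the either-test reading and on an assumed correlation between the two ERRs. The excess shrinks as that correlation rises, but remains at 0.95.

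What suffers is the weight a reader can put on a significant result. No decision to continue or stop modelling depends on it.

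A reader might also infer that the sample size is wrong. It is not: the figure of 32 reproduces for one test, which is what Section 6.2 describes.

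The interim Spearman test in Section 6.4 is a separate, earlier look and is not part of the 7–10%. The percentages above concern the final analysis alone.

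**What to change.** - In Sections 3.5.1, 6.1, 6.1.2 and 6.3, name 4 h ERR, already used in Sections 1.2.3 and 6.4, as the single predictor for the Spearman check at two-sided 0.05.
- Report the 24 h correlation as supportive, with its confidence interval.
- State that a significant 4 h result does not vouch for a model that relies on 24 h ERR, and label any such model exploratory. 24 h ERR can remain a candidate in model building on those terms.
- State that the choice of 4 h follows Sections 1.2.3 and 6.4 and does not depend on interim results. This needs saying because Section 6.4 reports that about two thirds of the projected subjects had already completed.
- Align the Précis so that the 2 h value is described as exploratory.

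**Cost.** Wording only; no extra subjects, and power at n = 32 stays at about 80%. The downside is that a significant 24 h result alone can no longer be presented as passing the check. If the sponsor wants either time point to count, testing each at 0.025 is the alternative, but it needs about 39 subjects for 80% power per test, close to the ceiling of 40.

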### **3.5.2. Secondary Endpoint**

Subjects will be classified into 3 categories on the basis of GC responsiveness: unresponsive, suboptimally responsive, and steroid-responsive. These categories are defined in Section 6.1 “Description of the analyses.”

Clinical factors associated with GC responsiveness (including HES variant, pattern of organ involvement and laboratory parameters) will be explored.

### **3.5.3. Exploratory Endpoints**

The mechanisms of GC resistance will be explored (Appendix F) by dividing subjects into response categories for the following assessment in all subjects:

- a) GI absorption of prednisone by evaluation of plasma levels of prednisone/prednisolone
- b) intracellular cytokine profiles in lymphocytes using multiparameter flow cytometry
- c) RNA expression profiles by microarray profiling of whole blood
- d) GR isoform assessments: GR isoforms will be assessed on all subjects using RT-PCR to understand relationship between responsiveness and predominant isoforms
- e) Proteomics: A collaboration with [name] (Assistant Professor, [name]) has been initiated using samples from the screening protocol for eosinophilia (94-I-0079). If preliminary findings are promising, coded samples, without personal identifying information, from 12-I-0026 will be sent to him for further proteomic evaluation of steroid responsiveness.

Not all studies will be performed for each subject due to time or sample constraints, although efforts will be made to proceed with exploratory investigations in a uniform manner. Additionally, investigations not outlined above may be performed based on preliminary findings and collaborations with other investigators in the field of GC responsiveness.

## **4. Inclusion and Exclusion Criteria**

### **4.1. Subject Inclusion Criteria**

Subjects on Protocol #94-I-0079 will be eligible for participation in the study only if all of the following criteria apply:

1. Subjects must be 7 years of age or older to enroll
2. Subject meets diagnostic criteria for HES (AEC >1500/ $\mu$ L, absence of a secondary cause and signs and/or symptoms attributable to the eosinophilia)
3. AEC >1500/ $\mu$ L obtained within 14 days prior to enrollment

4. Willingness to perform the timed steroid challenge
5. Appropriate candidate for GC treatment after challenge
6. Willingness to have samples stored for future research

## **4.2. Subject Exclusion Criteria**

A subject will not be eligible to participate in the study if any of the following apply:

1. Receiving >10 mg prednisone or equivalent at the time of enrollment.
2. Receiving ≤10 mg of prednisone or equivalent but have not been on a fixed dose for at least 3 weeks (subjects on a current corticosteroid taper will be excluded)
3. AEC ≤1500/μl on the day of the steroid challenge
4. Use of immunomodulatory medications, (other than ≤10 mg/day prednisone) including but not limited to biologics, within the past 6 months
5. Pregnant at the time of screening.
6. Have a known mutation in the FIP1L1-PDGFR gene
7. Any condition that, in the opinion of the investigator, places the subject at undue risk by participating in the protocol
8. Weight less than 48 kg (106 lbs) in subjects less than 18 years of age

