## **7. Human Subjects Protection**

### **7.1. Study Population**

#### **7.1.1. Rationale for Subject Selection**

New and returning subjects enrolled on Protocol #94-I-0079 who have documented HES, AEC >1500/ $\mu$ L on  $\leq$  10 mg prednisone equivalent daily and are candidates for GC therapy will be recruited for this protocol. Subjects receiving higher prednisone doses at baseline will be excluded to maximize the likelihood that the steroid challenge will have observable effects. Subjects with chronic eosinophilic leukemia, including those with PDGFR-associated disease, will also be excluded since imatinib is first line therapy for this condition.

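### Subjects on up to 10 mg prednisone at entry are pooled with steroid-free subjects, and no analysis takes entry dose into account

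*Combined protocol and SAP*

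**What the plan says.** **Who enters.** Section 4.2 rules out subjects "Receiving >10 mg prednisone or equivalent at the time of enrollment". Its second item admits lower doses only if they have been fixed for at least 3 weeks, and its third requires an absolute eosinophil count (AEC) above 1500/µL on the challenge day, whatever the entry dose. Section 7.1.1 gives the reason for the ceiling: "Subjects receiving higher prednisone doses at baseline will be excluded to maximize the likelihood that the steroid challenge will have observable effects".

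**The outcome.** Section 3.5.1 defines responsiveness mainly as the lowest prednisone dose that holds AEC below 1000/µL with symptoms controlled. Under Section 3.4 the taper can go down to 5 mg.

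**The predictors.** Section 6.3 restricts them to measurements from the first 24 hours after the initial dose. It says "These variables will be used to predict the GC responsiveness" and names the percent change in eosinophils at 4 and 24 hours and steroid absorption. Entry dose is known before dosing and is not on the list.

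**The tests.** Sections 6.1 and 6.3 plan an unadjusted Spearman correlation, with "Level of Significance to be Used: Two-sided 0.05". The interim model in 6.4 uses only a polynomial of log(ERR) at 4 hours. No section adjusts for entry dose, stratifies by it or plans a sensitivity analysis on it. The clinical factors in 3.5.2 do not name it.

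**The concern.** Section 6.1 gives the Spearman test one job: to guard against a model that seems to predict dose when nothing lies behind it. Entry dose could weaken that guard if it is tied to both variables.

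- *Tie to end dose.* A subject with AEC above 1500 after at least 3 weeks on a fixed dose has not met the below-1000 criterion at that dose. The end dose is therefore expected to lie above the entry dose, while a steroid-free subject can finish at 5 mg.
- *Possible tie to ERR.* The rationale in 7.1.1 accepts that background prednisone can mask the challenge effect. It says so for doses above 10 mg and gives no size at or below 10 mg.

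If both ties hold, a smaller eosinophil fall goes with a higher end dose even when the challenge carries no information. That is the direction the study hopes to find. It also bears on the purpose stated in Section 1.1, predicting the maintenance dose: entry dose is known without a challenge, so the challenge has to add something to it.

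**Working it through.** ERR is taken here as the size of the percent fall, so the hoped-for correlation with end dose is negative.

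**1. The plan's own figure.** Section 6.2 states the number of subjects "needed to show that the correlation is different from zero at the two-sided 0.05 level with 80% power is about 32 subjects". It reports that "the Spearman coefficient is significantly different from zero 79.5% of the time", and that the Pearson calculation "gives a sample size of 29 for the same situation". For Pearson, N = ((1.960 + 0.842) / atanh 0.5)² + 3 = (2.802 / 0.5493)² + 3 = 29.01. For Spearman, 100,000 simulated bivariate normal data sets at n = 32 give 80.0% power. Both figures reproduce, so the sample size is not at issue.

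**2. How pooling alone can produce a correlation.** Let a share f be on steroids at entry, with ERR lower and end dose higher by d SD each, and no association within either group. The pooled correlation is then

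r = −f(1−f)d² / (1 + f(1−f)d²).

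- f = 0.5, d = 0.5: −0.0625 / 1.0625 = −0.06. Simulated false-positive rate at n = 32: 6.4%.
- f = 0.25, d = 1: −0.1875 / 1.1875 = −0.16. Rate 13%.
- f = 0.5, d = 1: −0.25 / 1.25 = −0.20. Rate 20%.

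Both f and d are assumptions. The effect grows with d² and is negligible when d is 0.5 or less.

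**3. Using the protocol's entry and endpoint rules.** Here end doses lie on an assumed grid from 5 to 80 mg, each subject on steroids must end above the entry dose, and ERR is lower by 0.5 or 0.8 SD in that group. There is no association within groups. Simulated at n = 36, inside the planned 30-40, with 3,000 data sets per case:

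| Entry doses | End doses | Share on steroids | Shift 0.5 SD | Shift 0.8 SD |
|---|---|---|---|---|
| All 10 mg | Clustered low | 30% | 7.5% | 12.6% |
| All 10 mg | Clustered low | 50% | 10.5% | 16.8% |
| Mixed 2.5-10 mg | Clustered low | 30% | 5.4% | 6.8% |
| Mixed 2.5-10 mg | Clustered low | 50% | 5.9% | 8.5% |

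With all entrants at 10 mg and end doses spread evenly, the rate is 5.6-6.9%. With 10% on steroids it is 4.9-6.5% throughout. With no ERR shift it stays at 5% in every setting. The top figure depends on how end doses cluster: another set of low-clustered weights, at n = 32-40 with the same shares and shifts, gave 9-22%.

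**4. The adjusted test.** The partial Spearman correlation is

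r(xy·z) = (r_xy − r_xz r_yz) / √[(1 − r_xz²)(1 − r_yz²)],

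computed on ranks and tested by t on n − 3 degrees of freedom. Given on/off steroid status at entry, its false-positive rate was about 4-6% in all these settings. A check with the ranked entry dose in place of on/off status also stayed near 5%.

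**5. Its power.** With a within-group correlation of 0.5 in absolute value, power is about 78.5% at n = 32 (80.0% unadjusted), about 81% at n = 34 and about 88% at n = 40.

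**The case against.** A reader might infer that entry dose is a proven common cause and that any correlation found would be spurious. The documents do not support that.

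- Section 7.1.1 concerns doses above 10 mg. It shows no blunting at or below 10 mg against a 1 mg/kg challenge. ERR is measured against each subject's own baseline, and the 10 mg ceiling and 3-week fixed dose are the design's response. This stands: the ERR shift is a possibility, and without it there is no inflation.
- Still being above 1500 on a fixed dose is partly early evidence of poor responsiveness, the trait ERR is meant to predict. Some of the shared variation may be real signal that adjustment would remove. This also stands. In simulations at n = 32 with a true correlation of 0.5, entry status tied to end dose and no effect of entry steroid on ERR, adjustment lowered power from 75-77% to 68-74% with 30% on steroids, and from 70-72% to 60-65% with 50%. It is a reason to report both results, not to replace one with the other.
- The study calls itself exploratory, and under 6.1.2 modelling goes ahead whatever the test shows, so no decision hangs on the p-value. This lowers the stakes, but readers will still take a significant correlation as evidence that the challenge predicts dose.
- The class of linear models in 6.1 and the open-ended list of clinical factors in 3.5.2 do not forbid entry dose. True, but neither plans for it, and the predictor definition in 6.3 leaves it out.

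**Conclusion.** The omission is confirmed, and its effect is possible but not established. Pooling without regard to entry dose leaves open whether an ERR-dose correlation shows what the challenge adds or what was already known at entry.

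For assumed shares of 10-50% on steroids and assumed ERR shifts of 0.5-0.8 SD at about 36 subjects, the false-positive rate runs from about 5% to about 16-17% against a nominal 5%. The lower end applies with few subjects on steroids, mixed entry doses or evenly spread end doses. The upper end needs half on steroids, all at 10 mg, and end doses clustered low; tighter clustering or larger shifts would raise it. The documents supply neither the share nor the shift, so no single figure in this range should be read as expected.

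The stated sample size is not wrong, and the planned 30-40 subjects can carry one extra covariate.

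**What to change.** - **Section 6.3:** keep the unadjusted Spearman correlation and report beside it, with a confidence interval, the partial Spearman correlation given entry prednisone dose.
- **Section 6.1:** allow entry dose as a candidate predictor, and widen the predictor definition in 6.3 to admit this one pre-dose value. The added value of ERR over entry dose can then be judged.
- **Reporting:** give the distribution of entry doses. Show the steroid-free subset descriptively only. With 30% or 50% on steroids it would hold about 22 or 16 of 32 subjects (32 × 0.7; 32 × 0.5), with about 63% or 47% power at a correlation of 0.5.

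**Cost.** This changes analysis wording only. Eligibility already turns on entry dose, and Appendix B collects a medication history at baseline. Adjustment uses one degree of freedom, about 1-2 points of power at 32 subjects or 1-2 more subjects to recover it. The loss is larger, and some real signal may go, if entry dose itself reflects responsiveness; reporting both correlations lets the reader see that.
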